##### Exclusion Criteria

1. Women who are pregnant, nursing or of childbearing potential and not practicing an effective means of birth control (not including hormonal contraceptives).
2. Women who are currently taking, or have taken in the past month, oral or other types of hormonal contraceptives or hormone replacement therapies.
3. Women with premenstrual dysphoric disorder who are outside of the follicular phase.
4. Women who have had a complete hysterectomy or are over 50 over one year post-menopausal, as ovarian hormones will be measured in the study.
5. Subjects with evidence of or a history of significant hematological, endocrine, cardiovascular, pulmonary, renal, gastrointestinal, or neurological disease including diabetes, as these conditions may affect physiological/subjective responses. Neurological exclusions include history of stroke, seizure disorders, multiple sclerosis, Parkinson's disease, and Alzheimer's disease.
6. Subjects with Addison's disease, Cushing's disease or other diseases of the adrenal cortex likely to affect hormonal/neuroendocrine status.
7. Subjects with a history of or current psychotic disorder or bipolar affective disorder as these may interfere with subjective measurements.
8. Subjects with current major depressive disorder or post-traumatic stress disorder as these disorders are associated with characteristic changes in stress response.
9. Subjects receiving synthetic glucocorticoid therapy, any exogenous steroid therapy, or treatment with other agents that interfere with hormonal measurements within one month of test session.
10. Subjects taking any mood stabilizers, antipsychotics, benzodiazepines, opiates or opiate antagonists because these may affect test response. Subjects taking SSRI's will be included.
11. Subjects with any acute illness or fever. Individuals who otherwise meet study criteria will be rescheduled for evaluation for participation.
12. Subjects whose height to weight ratio would preclude them from fitting comfortably in the MRI scanner.

13. Subjects who are unwilling or unable to maintain abstinence from alcohol and other drugs of abuse (except nicotine) for three days prior to the stress task procedure.
14. Persons with ferrous metal implants or pacemaker since fMRI will be used.
15. Subjects who are claustrophobic.
16. Subjects with significant psychiatric or medical problems that would impair participation or limit ability to participate in scan.
17. Subjects who require maintenance or acute treatment with any psychoactive medication including anti-seizure medications which could potentially interfere with fMRI.
18. Subjects meeting DSM-IV criteria for substance dependence (other than nicotine, cocaine, alcohol or marijuana) within the past 60 days.

#### **b. Sources of Materials**

Research material obtained from individual subjects includes questionnaires and interviews with study personnel, saliva and urine samples, as well as structural and functional MRI scans. To ensure confidentiality, all subject data will be letter/number coded, and only the investigators will have access to the master lists of codes. The research material will be obtained specifically for research purposes. Written research material obtained will be stored in the Addiction Sciences Division, in an office that is locked when not in use. Saliva and urine samples will be stored in the Research Nexus and the Clinical Neurobiology Laboratory. Neuroimaging data will be stored on a secure password protected server maintained by MUSC's Center for Advanced Imaging Research.

#### **c. Potential Risks**

Adverse effects associated with systemic oxytocin use in pregnancy may include seizures, mental disturbances, unexpected bleeding or contraction of the uterus. However, several studies have been conducted in humans with intranasal doses between 20 and 60 IU, and no side effects have been reported (Bruins, Hijman, & Van Ree, 1992; Fehm-Wolfsdorf, Bachholz, Born, Voigt, & Fehm, 1988; Pitman, Orr, & Lasko, 1993). A recent review by MacDonald and colleagues (2011) also found no adverse outcomes associated with oxytocin dosages of 18-40 IU for short term use in controlled research settings. Exposure to cocaine and negative emotional cues may produce some craving for cocaine or other discomfort. However, this discomfort is usually brief and subjects will be in the cocaine-free safety of a clinic environment. Since the scanner requires subjects to be motionless in an enclosed environment, there is the possibility of a claustrophobic reaction or anxiety or discomfort secondary to being stationary for 45-60 minutes per scan. Ferrous objects in the body that are undetected could move during scans. This could lead to tissue damage and hemorrhage. For patients who consent to genetic testing, there is the possibility of complications from venipuncture such as mild pain and possible bruising at the needle site.

## **2. ADEQUACY OF PROTECTION AGAINSTS RISKS**

#### **a. Recruitment and Informed Consent**

Patients will primarily be recruited through the use of advertisements (internet, newspaper). The study PI, a Co-I, or other qualified study staff will obtain informed consent. The informed consent form includes a detailed description of the study procedures, along with statements regarding participants' rights to withdraw from the procedure at any time without consequences. The informed consent form will be explained to subjects in easy-to-understand language, and subjects will be instructed to read the form carefully prior to signing it. Consent will be documented by the signature of the participant on the informed consent agreement, accompanied by the signature of the individual obtaining the consent.

**b. Protections Against Risks**

All study participants will be closely monitored for psychiatric and medical stability. Patients in acute distress, including those endorsing suicidal ideation, will be seen by one of the psychiatrists in our division prior to being discharged. If the psychiatrist determines that the subject is in immediate danger, arrangements will be made for inpatient hospitalization at the Center for Drug and Alcohol Programs. Subjects who do not pose an immediate threat to self or others will be referred for services at the Center for Drug and Alcohol Programs, or a community mental health department if appropriate. The instrumentation used for physiological recordings meets all safety standards for non-invasive recordings, and participants are located out of reach of any AC-powered devices in the laboratory. All sessions will be conducted under the supervision of experienced personnel. If crisis intervention is necessary, senior staff will be available to evaluate the subject and provide an intervention or referral. If hospitalization is indicated, the patient will be hospitalized through the Center for Drug and Alcohol Programs at MUSC or an appropriate referral will be made. All subjects will be fully informed that they may withdraw from the experiment at any time without penalty. All subject records will be kept in a locked filing cabinet, and confidentiality of all materials will be maintained. Offices also will be locked at times when not in use. Neuroimaging data are coded and maintained on a password protected server.

To ensure confidentiality, all subject data will be coded by letters and/or numbers, and only the investigators will have access to the master lists of codes. All patient records will be kept in an office that will be locked at times when not in use. The research staff understands the importance of maintaining confidentiality. This method of maintaining confidentiality has been used for several years by our research group and has been effective. All co-investigators and study personnel have completed (or will complete upon hiring) training in Good Research Practices as mandated by the MUSC IRB.

Subjects will be taught about potential side effects of oxytocin, and will be closely followed by psychiatrists, a PharmD, and other members of the research team. Pregnancy tests will be performed on the day of oxytocin administration. Oxytocin administration will occur in a fully staffed clinical environment with emergency medications (i.e., IM diphenhydramine, alprazolam) and equipment available as needed. Adverse events will be monitored throughout the study. If abnormalities in the brain images are found, the subjects will be immediately referred to an appropriate clinical care provider. A careful metal screening history will be taken from each subject to assess the possibility of metal devices and individuals will be screened with a metal detector for the possibility of implanted metal objects since magnetic movement of a metal device or metal object could well result in injury or risk to life. Prior exposure to pictures of the scanner, getting into the scanner, and seeing others in the scanner often reduces psychological discomfort or identifies people for whom scanning is not appropriate.

**3. POTENTIAL BENEFITS OF THE PROPOSED RESEARCH TO THE SUBJECT AND OTHERS**

Possible risks to study participants include adverse reactions to oxytocin administration. Benefits include detailed assessment of substance use and referral for treatment. While the benefits to the individual patient are minimal, the minimal risks are reasonable in relation to the benefits to be gained from the investigation. An investigation of oxytocin's effects on stress- and cue-induced craving may provide important information that can guide treatment for future patients with cocaine dependence.

**4. IMPORTANCE OF THE KNOWLEDGE TO BE GAINED**

This study may provide important information that can improve treatment for future patients with cocaine and other drug dependence. The minimal risks of the investigation are considered reasonable in relation to the expected knowledge to be gained.

## **5. DATA AND SAFETY MONITORING PLAN**

This section is based on the recommendations in NIDA's "Guidelines for Developing a Data and Safety Monitoring Plan" ([www.drugabuse.gov/funding/dsmbosop.html](http://www.drugabuse.gov/funding/dsmbosop.html)). A detailed DSMP will be developed and approved by NIH program staff prior to study initiation.

### 5.1 Summary of the Protocol.

This application proposes to investigate the effects of oxytocin on stress and cue induced reactivity in cocaine-dependent individuals, and whether gender differences in response exist. The primary outcome of interest is craving and stress response to the interventions. Inclusion/exclusion criteria are outlined above. Power calculations and sample sizes are in the Data Analysis Plan section above.

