**Title: Oxytocin in Cocaine Dependence**

**NCT: 01573273**

**Date of Document: 8/1/2016**

## Oxytocin in Cocaine Dependence

### SPECIFIC AIMS

Previous work conducted by the MUSC SCOR identified sex/gender differences in preclinical and clinical models of cocaine cue and stress reactivity that may contribute to gender differences in relapse. The proposed project will build on this work by exploring potential mechanisms for these sex/gender differences. Specifically, several studies have indicated that hypothalamic neuropeptides mediate behavioral responding to stress as well as play a role in neuroadaptations that occur as a consequence of long-term cocaine use. The hypothalamic neuropeptide oxytocin promotes trust, social bonding, and calmness. Given these effects, oxytocin may have a therapeutic role in ameliorating the negative affect commonly observed prior to relapse in cocaine-dependent individuals. As estrogen appears to enhance oxytocin's effects, women may have an enhanced response to oxytocin. The specific aims of the proposed project are:

**Specific Aim 1: Using a human laboratory paradigm, determine the impact of oxytocin on stress-induced craving in cocaine-dependent women and men.**

Preclinical and clinical investigations have found that the neuropeptide oxytocin exerts anxiolytic effects in stress paradigms. However, little is known about the potential anxiolytic effects of oxytocin in cocaine-dependent individuals, or if a gender differential in response exists.

**Hypothesis 1a:** Intranasal administration of oxytocin will attenuate drug craving response and stress reactivity to a psychosocial stress task in cocaine-dependent individuals compared to placebo administration.

**Hypothesis 1b:** The ameliorative effects of oxytocin on drug craving response and stress reactivity will be more pronounced in cocaine-dependent women as compared to cocaine-dependent men.

**Exploratory Hypothesis 1c:** The stress and craving reduction induced by oxytocin in women will be related to estrogen and progesterone levels.

**Specific Aim 2: Using a neuroimaging cue paradigm, explore the impact of oxytocin on neural correlates and subjective responses of cocaine cue reactivity in cocaine-dependent men and women.**

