3. **Assessments.** All baseline and within-session measurements have been previously used by our research group. Wherever possible, the same assessment instruments will be used in Project IV to foster cross-study analysis and comparison (i.e., psychiatric assessment, trauma history). . **Urine Drug Screening:** Drug screens will be performed using the *iCup*® DX Drug Screen Cup, an in vitro diagnostic test for the qualitative detection of drug or drug metabolite in the urine. The test profile consists of amphetamines, d-methamphetamine, cocaine, opioids, , THC and benzodiazepines. Results will be used to ascertain abstinence prior to initiation of test sessions and to substantiate self-reports. **Breathalyzer:** Participants will have their breath sampled for the presence of alcohol (Alco-Sensor III, Intoximeters Inc., St. Louis, MO). **Self Report Measures. Within Session Rating Scale:** A modification of the Within Session Rating Scale (Childress, McLellan, & O'Brien, 1986a) will be used to assess craving and mood during the procedure. This 100 mm visual analogue scale is anchored with the adjectival modifiers (“not at all, mildly, moderately, and extremely”). The scale includes items assessing anxiety, stress, anger, irritability, and depressed mood. **State-Trait Inventory (STAI):** The STAI is a 20-item self-report scale (Spielberger, 1983) employing a Likert-scale format with four responses per item (1-4). Ten of the STAI items measure feelings of stress and anxiety, while the remaining ten items measure feelings of relaxation. The STAI has good psychometric properties. **Cocaine Craving Questionnaire-Brief (CCQ-Brief):** The CCQ-Brief is a 10-item scale derived from the Cocaine Craving Questionnaire (Tiffany et al., 1993) and demonstrated to be a valid and reliable measurement of current cocaine craving (Sussner et al., 2006). **Physiological Measures.** Heart rate and blood pressure will be measured using an intermittently inflatable cuff as indices of physiological arousal during the test session. **Hormonal Measures. Cortisol:** Cortisol will also be measured in unstimulated passive saliva using the Salimetrics expanded range, high sensitivity salivary cortisol enzyme immunoassay kit. This kit has a lower sensitivity level of <0.003 µg/dL. The correlation between salivary and serum cortisol has been shown to be high ( $r=0.91$ ,  $p<0.0001$ ). Cortisol is commonly measured as an indication of stress response in human laboratory studies. **Progesterone:** Progesterone will be measured from a salivary sample tested using the Salimetrics salivary progesterone enzyme immunoassay kit. The lower limit of sensitivity is 5 pg/ml, and the correlation between serum and saliva is highly significant ( $r=0.80$ ,  $p<0.0001$ ). **Estradiol:** Estradiol will be measured from a salivary sample tested using the Salimetrics 17β-estradiol enzyme immunoassay kit collected in EDTA-tubes and processed using a chemiluminescent immunoassay. The lower limit of sensitivity is 0.1 pg/ml, and correlation with serum is high ( $r=0.80$ ,  $p<0.001$ ).

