**C.2.d. Statistical Methods.** The hypotheses associated with Aim 1 are interested in the effect of oxytocin on cocaine craving and stress in response to the TSST. It is hypothesized that cocaine-dependent participants receiving oxytocin will demonstrate greater attenuation of stress and craving response to TSST as compared to those receiving matched placebo. A linear mixed effects model containing all serially measured time points will be used to assess the effects of oxytocin versus placebo on each dependent variable. Restricted maximum likelihood (REML; Patterson and Thompson, 1971) methods will be used to estimate the fixed effects and variance components, and baseline values will be used as covariates in the regression models. To test the hypothesis that women will experience greater ameliorative effects of oxytocin on stress and craving response following the TSST as compared to males, similar models will examine the differential (interaction) in the scores reported between men and women by treatment group (oxytocin vs. placebo). Additionally, as an exploratory analysis, the strength of the effects of oxytocin in women will be assessed with differences in estrogen and menstrual cycle phase as independent variables. In a subgroup analysis of women entered into the study, linear mixed effects models will be developed to assess the association of estrogen and menstrual phase (independently) on the stress and craving response to the TSST. Non-linear associations will also be explored using cubic spline models (Marrie et al., 2009). Within each family of dependent measures, the Type I error rate will be controlled using a post-hoc Bonferroni correction.

The hypotheses associated with Aim 2 are concerned with the impact of oxytocin on cocaine cue reactivity. It is hypothesized that oxytocin will decrease cue-induced cocaine craving in cocaine-dependent men and women compared with placebo administration. Post-acquisition preprocessing and statistical analysis will be performed using Matlab 7.8 (Mathworks, Sherborn, MA) with Statistical Parametric Mapping software 8

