**C.2.e. Power and Sample Size.** *Aim 1.* It is hypothesized that oxytocin will decrease ratings of subjective stress and cocaine craving following the TSST relative to placebo. Pilot data suggests an expected between group mean differences in total cocaine craving (CCQ) following the TSST of  $\Delta = 8.24$  with a RMSE = 11.03 ( $d = 0.75$ ) (Cohen, 1988) and a stress rating (VAS) difference of  $\Delta = 1.07$  with a RMSE = 2.20 ( $d = 0.49$ ). As in the oxytocin pilot study, participants will be assessed at four post TSST time points ( $m$ ), with an anticipated intraclass correlation coefficient of 0.78 for both craving and stress outcomes (ICC = 0.78 & 0.79, respectively). The design effect, which accounts for the multiple correlated observation within each subject, is estimated to be 3.35 (DE =  $[1 + (4-1)0.78]$ ) (Donner and Klar, 2000). Assuming independent observations and an effect similar to the pilot data for the stress response ( $d = 0.48$ ), the total effective sample size would be 140 subjects (35 men and 35 women per treatment arm) to provide 80% power with a type I error rate of 0.05. In a clustered setting, the sample size is  $N_{\text{effective}} = nm/DE$  where  $n$  is the number of participants required when  $m$  replications within participants are performed after accounting for the design effect (DE). For the study at hand, the total

Version 16.0 (Revised 08/01/2016)

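### Hypothesis 1a has two primary constructs but no deciding measure, family list or success rule, so its type I error is undetermined, and the within-family Bonferroni conflicts with powering at 0.05

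*Combined protocol and SAP*

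**What the plan says.** - **Primary outcome.** Section 5.1: "The primary outcome of interest is craving and stress response to the interventions". It gives no scale, time point or success rule.
- **Hypothesis.** Hypothesis 1a in the Specific Aims: "Intranasal administration of oxytocin will attenuate drug craving response and stress reactivity to a psychosocial stress task in cocaine-dependent individuals compared to placebo administration".
- **Measures.** The Assessments part of section C.2.c.2 offers several candidates per construct. Craving has the CCQ-Brief and the Within Session Rating Scale, which "will be used to assess craving and mood during the procedure". Stress has the stress and anxiety items of that scale, the STAI, cortisol, heart rate and blood pressure.
- **Analysis.** Section C.2.d uses a linear mixed model over all time points with baseline covariates "to assess the effects of oxytocin versus placebo on each dependent variable". On multiplicity it says "Within each family of dependent measures, the Type I error rate will be controlled using a post-hoc Bonferroni correction". The families are not listed or counted, and no rule operates between them.
- **Power.** Section C.2.e takes pilot differences for two measures: CCQ total craving (d = 0.75) and a stress VAS (d = 0.49, then 0.48 for the sample size). It sizes the trial on stress "to provide 80% power with a type I error rate of 0.05". It claims 80% power for stress and 98% for craving with 120 completers. Section C.2.d does not make these two measures the deciding tests.

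**The concern.** Two things are left open. The first is what counts as support for Hypothesis 1a: which instrument stands for each construct, and whether one construct or both must show an effect. The second is the boundary of each family, which fixes both the threshold every test must meet and the error rate over all of them. The correction is described as post-hoc, so nothing commits the sponsor to a grouping before the data are seen.

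The conclusion could turn on these choices. Section C.1.b reports a pilot in which craving gave p = 0.025 and cortisol p = 0.066. That pilot had 16 marijuana-dependent participants, and cortisol is not one of the two powered outcomes. It illustrates that candidate measures can fall on opposite sides of 0.05; it does not show that the two powered measures disagree.

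There is also an internal conflict. The sample size assumes each powered measure is tested at 0.05, while the analysis section promises a stricter threshold for any measure that shares a family.

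**Working it through.** **1. The plan's own sample size.** Inputs from C.2.e: d = 0.48, 80% power, type I error 0.05, four post-task assessments, design effect stated as 3.35.
- Two-sided 0.05 with equal arms gives 69 per arm (138 in total) by the normal formula and 70 per arm (140) by the t-test. The stated 140 is reproduced. One-sided 0.05 gives 108, which does not match.
- 140 × 3.35 / 4 = 117.25, rounded up to 118, as stated.
- So stress was powered at two-sided 0.05 with nothing deducted for multiplicity. (The bracketed formula 1 + 3 × 0.78 gives 3.34, not 3.35; this is immaterial here.)

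**2. Type I error for Hypothesis 1a under each possible reading.** The number of families and the correlations between tests are assumptions, because the plan gives neither.

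| Reading | At least one false positive, two-sided | In oxytocin's favour only |
|---|---|---|
| Both constructs must be significant, or all measures form one family | at most 0.05 | at most 0.025 |
| Two families at 0.05, either suffices, independent | 1 − 0.95² = 0.0975 | 1 − 0.975² = 0.049 |
| Same, correlation 0.5 | 0.091 | 0.045 |
| Same, correlation 0.7 | 0.083 | 0.042 |
| Same, correlation 0.8 | 0.078 | 0.039 |
| Three families, either suffices, independent | 1 − 0.95³ = 0.143 | 1 − 0.975³ = 0.073 |

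The two-family figures treat each family as one test at 0.05. Bonferroni over correlated measures within a family would lower them. The two-sided upper bound for two families is 0.10.

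**3. Power for the stress rating if Bonferroni is applied as written.** With 120 completers, the effective sample size on the plan's design-effect basis is 120 × 4 / 3.35 = 143.3. The expected test statistic is 0.48 × √(143.3 / 4) = 2.873. Power is Φ(2.873 − z), where z is the two-sided critical value at 0.05/k and k is the assumed number of measures in the family.

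| k | z | Power |
|---|---|---|
| 1 | 1.960 | 82% |
| 2 | 2.241 | 74% |
| 3 | 2.394 | 68% |
| 6 | 2.638 | 59% |

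The value k = 6 would cover the stress item, anxiety item, STAI, cortisol, heart rate and blood pressure. Craving is little affected: at k = 2 its power is 98.8% on the same basis.

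**4. Cost of a fixed sequence.** If stress is tested only after craving succeeds, the stress power lost cannot exceed the chance that craving fails. Craving power is 99.4% on the design-effect basis and 98.4% with 60 per arm and no design effect. The loss is therefore at most 0.6 or 1.6 percentage points. By comparison, an even split at 0.025 each would cut stress power from 82% to 74%.

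**The case against.** A reader might infer that the plan allows oxytocin to be declared effective at about twice the stated 0.05. The documents do not support that. It needs craving and stress to be separate families, which C.2.d never says, and success on either to be enough, whereas Hypothesis 1a joins the two with 'and'. Even granting both premises, Hypothesis 1a is directional. With two families the chance of a false result in oxytocin's favour is 0.049 or less; the 0.0975 also counts false findings of harm, which would not support the hypothesis. That rate is still double the 0.025 of a single test in that direction. Nor is twice a ceiling: three or more families would exceed it.

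It would also be too strong to say that no contrast is specified. C.2.d names the treatment comparison, the model, the time points and the baseline adjustment.

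Section 5.9 says the study is not an intervention trial, and the background describes its therapeutic aim as preliminary. For a laboratory study, error control within families can be defended. That lowers the stakes, but it does not supply the missing family list or success rule, and it does not reconcile the correction with the power calculation.

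**Conclusion.** The concern holds in conditional form. The documents do not settle the type I error for Hypothesis 1a: it is at most 0.05 under two readings, 0.08 to 0.10 two-sided under a third (correlations from about 0.8 down to 0), and about 0.14 with three independent families (about 0.07 in oxytocin's favour). No single figure should be presented as the plan's error rate.

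The conflict with the power section does not depend on the success rule. Whenever the stress rating shares a family with other measures, the promised 80% is not met at 120 completers: about 74% with two measures and 59% with six. These figures rest on assumed family sizes, on d = 0.48 and on the plan's own design effect.

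This does not invalidate the trial, but it should be corrected, because the main claim has no prespecified decision rule and the repair is nearly free.

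**What to change.** In sections C.2.d and 5.1, for the stress task (Aim 1):

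1. Name two deciding measures for Hypothesis 1a: CCQ total craving, stating that this is the CCQ-Brief total, and the stress VAS. Both are already powered in C.2.e.
2. Define each test as the oxytocin-minus-placebo contrast from the mixed model, averaged over the four post-task time points.
3. State one decision rule. Either test in fixed sequence at two-sided 0.05, craving first and stress only if craving is significant; or, if the 'and' in Hypothesis 1a is meant literally, require both to be significant at 0.05. Craving first fits Aim 1, which is framed around stress-induced craving, and the Design Considerations section, which treats craving as a main outcome. The order remains the sponsor's choice.
4. Label the craving VAS, the other VAS items, STAI, cortisol, heart rate, blood pressure and all single time points as supportive, and list any families kept for them.

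The cost is a few sentences, with no new data or participants. Under the sequence, stress cannot be claimed if craving fails, which costs under 2 percentage points of stress power at the planned effects. Section 5.1 also covers the response to drug cues, so the corresponding rule for Aim 2 would need its own sentence.
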